2.4 Defintion of other feasibility outcomes

2.4.1 Feasibility and acceptability of data collection tools: will be measured by proportion of patients randomised with complete patient-related outcome data at 3 months follow up.

The following proposed patient outcomes will be collected at baseline (pre-randomisation) and 3 months follow up (post randomisation)*:

- HRQoL: EuroQoL (EQ-5D-5L)
- Exercise/functional capacity: incremental shuttle walk test (ISWT);
- 4 Metre Gait Speed (MGS)
- Strength: Hand Grip Strength
- Mood: Patient Health Questionnaire-9 (PHQ-9);

PERFORM FEASIBILITY Protocol

Version 2.0 16.MAY.2023

- Generalised Anxiety Disorder Assessment-7 (GAD-7)
- Physical activity: International Physical Activity Questionnaire (IPAQ)
- Frailty: Functional Assessment of Chronic Illness Therapy; Fried Exhaustion and Weight Loss
- Fatigue (FACIT-F)
- Pain: Brief Pain Inventory (BPI)
- Health and disability: WHODAS
- Breathlessness: Dyspnoea-12
- Sleep: Medical Outcome Study Sleep Scale (MOS Sleep Scale)
- Cognition: MoCA
- Multimorbidity Treatment Burden Questionnaire (MTBQ)
- ICEpop CAPability Measures for Adults (ICECAP-A)
- Clinical events mortality & hospital admissions (& primary care contacts); and social and healthcare utilisation (including medication (assess at follow up only))

The following proposed patient outcome will only be collected at 3 months follow up (post randomisation)*:

Exercise adherence: Exercise Adherence Rating Scale (EARS)

*This list of patient outcomes will be finalised following stakeholder consultation that forms part of WP2 and any changes will be submitted as an ethics amendment.

2.4.2 Estimates of key cost drivers.

Details are provided in the economic evaluation section (section 9).

2.4.3 Risks of bias/contamination.

Any outcome assessor blind breaks will be recorded. Contamination will be assessed by asking control participants to report whether they knew anyone in the intervention arm of the trial and whether they had access to any intervention resources.

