2.4.4 Further refine the intervention and programme theory

This will be completed at end of WP3 using data primarily from the process evaluation.

2.4.5 Feasibility and acceptability of data collection tools:

The proportion of 60 feasibility study patients with complete outcome data at 3-month follow up. Information on perceived outcome completion burden will be collected in patients interviews (see process evaluation, section 9).

2.4.6 Feasibility, acceptability of the intervention exploring barriers and facilitators to uptake and engagement from both participant and healthcare provider perspectives.

This will be assessed through qualitative interviews with patients and PERFORM intervention providers – see process evaluation section. This will also be assessed based on the adherence to the intervention (i.e. number of sessions attended out of the intervention program); adherence will be measured for each individual participant, which will be collected using attendance registers taken at each exercise session.

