The Medical Outcome Study Sleep Scale (MOS Sleep; Hays et al., 1992 [58]) is a 12item questionnaire that assesses sleep disturbance, sleep adequacy, somnolence, quantity of sleep, snoring, and awakening short of breath or with a headache.

Cognition

- The Montreal Cognitive Assessment

The Montreal Cognitive Assessment (MoCA; Nasreddine et al., 2005 [59]) is a 30-point cognitive screening test designed to help detect mild cognitive impairment and Alzheimer's disease. It includes items that assess short-term memory, visuospatial abilities, orientation, executive function, concentration, attention, and working memory. Time to complete: 10 minutes

Physical activity

- International Physical Activity Questionnaire (IPAQ)

The international physical activity questionnaire (Craig et al., 2003 [60]) is a self-reported measure for physical activity. To complete the measure individuals must recall their physical activity from the past 7 days.

Time to complete: 5 minutes

Treatment burden

- Multi-morbid treatment burden questionnaire (MTBQ)

The Multi-morbidity Treatment Burden Questionnaire (MTBQ; Duncan et al., 2020 [61]) is a 10-item questionnaire that aims to measure treatment burden in patients with multi-morbidity.

Time to complete: 5 minutes

Frailty

Fried exhaustion & weight loss

Self-reported exhaustion will be assessed using 2 questions from the Center for Epidemiologic Studies Depression (CERS-D) scale. Weight loss will be assessed as self-reported unintentional weight loss in the last year. For this, patients will be asked if they have unintentionally lost more than 4.5kg in the last 12 months. These measures are part of the Fried frailty assessment (51).

Time to complete: 5 minutes

Capability and wellbeing

ICEpop CAPability measure for Adults (ICECAP-A)

The ICEpop Capability Measure for Adults (ICECAP-A; Al-Janabi et al., 2012 [62]) measures 5 capabilities (stability, attachment, autonomy, achievement, and enjoyment) that are important to quality of life.

Time to complete: 5 minutes

• Exercise adherence

- Exercise Adherence Rating Scale (EARS)

The Exercise Adherence Rating Scale (EARS; Newman-Beinart et al., 2017 [63]) includes 6 items that directly assesses adherence behaviour. The EARS is scored on a 5-point Likert scale from 0 (completely agree) to 4 (completely disagree). Items 1, 4 and 6 are reverse scored, resulting in a score between 0 and 24. A higher score indicates better exercise adherence.

Time to complete: 5 minutes

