6.8.3 Follow-up assessments

Follow up will be undertaken at 3-month follow up (3 months post randomisation).

 All measures identified above will be repeated. All outcome measures will be conducted by a blinded assessor who will have no knowledge of previous test results or treatment allocation.

6.8.4 4 and 6 month group maintenance sessions

Patients randomised to the PERFORM intervention exercise programme will be invited to attend 2 group maintenance sessions at 4 months post randomisation and 6 month post randomisation. These sessions will provide an opportunity provide additional support to participants, review long-term progress and address any further questions they may have.

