7.2 Control group

Both intervention and control groups will receive usual care, i.e. continue to manage their disease as advised by their primary/secondary care team. This will be continuation with usual medication and follow up visits at either primary or secondary care as scheduled. After the initial assessment, patients allocated to control will continue with their usual care alone.

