10.2.3 Secondary outcome analysis

The number and proportion of patients randomised with complete data for each of the follow-up outcomes (possible outcomes for the subsequent definitive trial) measured at 3 months follow up will be calculated in all randomised patients and by randomised group.

Patient reported outcomes at 3 months follow up and the number of each of the clinical events within 3 months follow up will be summarised by randomised group and overall using mean (standard deviation) and median (interquartile range) for continuous variables and count (percentage) for categorical variables. Intervention-control between group mean differences and 95% CIs will be reported. Given the feasibility objectives of the study, no P-values will be reported.

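### The Exercise Adherence Rating Scale (EARS) is collected and compared in both arms, but only the intervention arm is prescribed exercise, and the protocol contradicts itself on whether EARS is also a baseline measure

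*Protocol*

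**What the plan says.** Section 2.4.1 introduces EARS with "The following proposed patient outcome will only be collected at 3 months follow up (post randomisation") and names it as "Exercise adherence: Exercise Adherence Rating Scale (EARS"). No arm is specified. The same section says that feasibility of the data collection tools "will be measured by proportion of patients randomised with complete patient-related outcome data at 3 months follow up", and section 2.4.5 restates this as "The proportion of 60 feasibility study patients with complete outcome data at 3-month follow up".

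Section 6.8.1, headed as baseline assessments, also lists EARS. It says the scale "includes 6 items that directly assesses adherence behaviour" and gives a score range of 0 to 24. Section 6.8.3 says of the 3-month visit that "All measures identified above will be repeated", without distinguishing the arms.

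Section 7.1 gives the intervention arm individually prescribed aerobic and resistance exercise and a home programme. For controls, section 7.2 says: "After the initial assessment, patients allocated to control will continue with their usual care alone".

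Section 10.2.3 plans completeness for each follow-up outcome, in all randomised patients and by group. For patient-reported outcomes it adds: "Intervention-control between group mean differences and 95% CIs will be reported". EARS is excepted from neither.

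**The concern.** An adherence scale needs something to adhere to. In this trial that is the exercise prescribed within PERFORM, which controls do not receive. A control handed EARS at 3 months can do one of two things, and the protocol gives no instruction and no rule for a not-applicable answer.

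- **Answer it.** The score then refers to whatever exercise the participant has in mind. The planned mean difference sets adherence to PERFORM against adherence to something undefined.
- **Leave it blank.** The blank counts as incomplete data, and a tool that works in the arm it suits looks harder to collect than it is.

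This matters because feasibility of the data collection tools is a stated objective, and section 10.2.3 treats the follow-up measures as possible outcomes for the definitive trial. The baseline listing is a separate problem. Sites cannot follow both 2.4.1 and 6.8.1, and at the baseline visit, before randomisation, nobody has a trial programme to adhere to.

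**Working it through.** **Is there an arm limit anywhere?** The protocol marks such limits where it intends them. The Schedule of Procedures labels the maintenance sessions as being for intervention patients, and section 2.3 confines the attendance outcome to those randomised to PERFORM. The 3-month outcome questionnaires in the schedule, sections 2.4.1 and 6.8.3, and the analysis in 10.2.3 carry no such limit for EARS.

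**What does EARS measure?** Section 6.8.1 speaks of adherence behaviour. The title of the development paper (reference 63) specifies adherence to prescribed exercise. Sections 7.1 and 7.2 place the trial's prescription in one arm only. The exclusion in section 5.2 of anyone in a rehabilitation exercise programme in the last 6 months removes a recent programme as an alternative referent.

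**Inputs for the completeness ceiling**
- 60 patients, 40 intervention and 20 control, with 20% loss anticipated at 3 months (section 10.1). The 2:1 split reproduces: 60 × 2/3 = 40 and 60 × 1/3 = 20.
- f, the share of controls who complete EARS. The protocol does not give it, so it is taken as an assumption from 0 to 1.
- Every other form is assumed complete, so that the result is a ceiling.

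**Before loss to follow-up:** ceiling = (40 + 20f)/60.

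| f | Ceiling |
|---|---|
| 0 | 40/60 = 66.7% |
| 0.25 | 45/60 = 75.0% |
| 0.5 | 50/60 = 83.3% |
| 0.75 | 55/60 = 91.7% |
| 1 | 60/60 = 100% |

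**After the stated loss:** 20% of 60 is 12 patients, leaving 48. The protocol states the loss overall, not by arm. With I intervention and C = 48 − I control patients remaining, the ceiling is (I + fC)/60.

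- f = 0, all 12 lost from intervention: I = 28, so 28/60 = 46.7%.
- f = 0, loss of 20% in each arm: I = 32, so 32/60 = 53.3%.
- f = 0, all 12 lost from control: I = 40, so 40/60 = 66.7%.
- f = 1: 48/60 = 80.0%, wherever the losses fall.

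**Which figures this touches.** The formula applies to the all-randomised EARS row in 10.2.3. It applies to an all-outcomes proportion only if 2.4.1 and 2.4.5 mean complete on every tool. By arm, f = 0 would show 0/20 in controls.

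**Progression criteria.** Section 2.3 defines retention by complete EQ-5D data, and adherence by sessions attended in the intervention arm. Recruitment is a count against 60. None uses EARS.

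**If EARS is confined to the intervention arm:** its denominator is 40, and with 12 losses overall its ceiling lies between 28/40 = 70.0% and 40/40 = 100% (32/40 = 80.0% with equal loss). The all-patient ceiling for the remaining tools returns to 60/60 before loss and 48/60 = 80.0% after it.

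**The case against.** The strongest reply is that this is a missing label, not a decision to question the wrong arm. Section 8 places patient-reported exercise adherence among the process data during the intervention and cites the same EARS paper (as reference 67), although the item itself names the Progress Tracker diary. That makes an oversight plausible, but sites work from the text, and the text sets no limit.

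It can also be said that the population for each summary belongs in the statistical analysis plan and that the outcome list is only proposed. The first point is fair for the summaries. Who is handed a form, and when, is fixed by the protocol, and section 2.4.1 itself routes changes to the list through an ethics amendment.

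Several stronger readings are tempting, and the documents do not support them:

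- **Completeness is capped at two thirds.** That is only the f = 0 limit. Questionnaires can be supervised (section 6.8.1) and sites are asked to check completion (section 10.7), so some controls may well answer. For an all-outcomes figure it also needs the composite reading, whereas 10.2.3 analyses each outcome separately and by group, where a gap confined to EARS in controls would be visible.
- **At most 32/60 after loss.** This assumes equal loss in both arms, which the protocol does not state.
- **Control scores mean nothing.** Usual care under section 7.2 may include exercise advice, and the EARS items are not shown. What can be said is that the trial defines no referent for controls.
- **A wrong progression decision could follow.** No criterion uses EARS, no completeness threshold for tools is set, and no P-values are reported.

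**Conclusion.** The point holds in a limited form. As written, the plan would produce a between-arm EARS difference that cannot be interpreted, and an all-randomised EARS completeness figure that depends partly on how controls treat a form not meant for them. The ceiling on that figure is (40 + 20f)/60: 66.7% to 100% before loss, and 28/60 to 40/60 if no control answers and 12 patients are lost. It extends to an all-outcomes figure only on the composite reading of 2.4.1 and 2.4.5. The value of f and the split of losses by arm are assumptions. The conclusion on interpretability depends on neither; it rests on the construct named in the cited title and on exercise being prescribed in one arm only.

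The conflict between 2.4.1 and 6.8.1 over baseline collection stands on the text alone. Recruitment, retention and attendance are untouched, so this is a correction worth making, not a threat to the study's main decision.

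**What to change.** - In sections 2.4.1 and 6.8.3, state that EARS is completed at 3 months by intervention participants only.
- Summarise it in that arm, with the number randomised to intervention as the denominator for completeness.
- In section 10.2.3, exclude EARS from the between-group differences and from completeness in all randomised patients. Apply the same exclusion to the proportions in 2.4.1 and 2.4.5.
- Remove EARS from the baseline list in section 6.8.1.

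The cost is a wording amendment, carried into the statistical analysis plan, and the loss of control-arm EARS data. Little is given up, because IPAQ is already collected in both arms and compares physical activity directly. Controls have one form fewer, and no visit is added.

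EARS should stay at 3 months. Moving it to the intervention discharge appointment may look convenient, but it would change the stated time point, require a change to the Schedule of Procedures, and risk missing participants who did not finish the programme, whose adherence is of most interest.

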| | To assess the feasibility and acceptability of data collection tools. | Proportion of patients with complete outcome data at 3-month follow up and process evaluation patient interviews |
| | To obtain estimates of key cost drivers. | From economic evaluation |
| | To assess risks of bias/contamination. | Outcome blinding breaks and access to PERFORM intervention by control group |

FUNDING AND SUPPORT IN KIND

FUNDER(S)

NIHR PGfAR NIHR202020

ROLE OF TRIAL SPONSOR

The Sponsor of this research is the University of Leicester. The University of Leicester is registered as a research sponsor with the Department of Health and routinely takes responsibility as sponsor for research activities within the NHS.

ROLES AND RESPONSIBILITIES OF TRIAL MANAGEMENT COMMITEES/GROUPS & INDIVIDUALS

Programme Management Group (PMG)

Monthly trial management meetings will take place, comprising the Chief Investigators, coapplicants, members of Leicester Clinical Trials Unit (LCTU) and a Patient Advisory Group (PAG) representative. These operational meetings will provide continuous monitoring of key milestones and provide a vehicle to highlight issues, and discuss and agree resolutions. In addition to these monthly meetings, the CIs/members of the research team will meet regularly with the LCTU hub to discuss the day to day running of the programme (these will be virtual). The PMG will report to the Programme Steering Committee (PSC).

Public Advisory Group (PAG)

The PAG, consisting of Patient and Public Involvement (PPI) representatives, will have 11 meetings as part of the larger PERFORM programme grant, each in Glasgow and Leicester to advise on overarching trial set-up, patient-facing materials and the topic guide for the semi-structured interviews and provide input to all WPs (plus 5 PAG evaluation/study meetings). The PAG would meet approximately every 6 months of the PERFORM programme grant timelines to provide input to all WPs, advise on trial conduct and dissemination of results. The PAG will report to the PMG (which will carry on after WP3 completion).

[figure not shown]
The PAG will evolve through the lifetime of the project and recruit new members (trial participants) to support PAG activities and dissemination events having first-hand experience of the intervention.

Programme Steering Committee (PSC)

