2.1.2 Objectives

- To assess study recruitment and retention.
- To assess the feasibility, acceptability of the intervention exploring barriers and facilitators, to uptake and engagement from both participant and healthcare provider perspectives.
- To assess fidelity and reach of the intervention.
- To further refine the intervention and programme theory.
- To assess the feasibility and acceptability of data collection tools.
- To obtain estimates of key cost drivers.
- To assess risks of bias/contamination.
 - D: Design randomised controlled trial
 - P: Population People with mutiple long-term conditions (mutlimorbidity)
 - I: Intervention PERFORM intervention + usual care
 - C: Control usual care alone
 - O: Outcome(s) feasibility and acceptability of the PERFORM intervention and study methods
 - T: Time baseline (pre-randomisation) and 3-months post-randomisation

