4. TRIAL SETTING

The feasibility study will be conducted across four study sites.

The study sites will be centres that have an established cardiac or pulmonary rehabilitation programme that can be adapted to deliver the PERFORM intervention. The sites will offer supervised rehabilitation within either an acute hospital or a community service.

Patients will be recruited from both primary and secondary care pathways including cardiac and pulmonary registers and clinic lists, outpatient clinics, primary care referrals and other relevant pathways as outlined in section 6.2.

Follow-up procedures will be conducted on NHS premises. Conduct of the study will be led by a local principal investigator, supported by a research nurse/fellow and/or relevantly trained rehabilitation staff at each site, all of whom are trained in Good Clinical Practice and in the requirements of the study protocol.

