The questionnaires will be presented in a consistent order and completed under supervision or with a healthcare professional as necessary. There is an opportunity to complete a number of assessments in between the practice and repeat ISWT. It is planned to complete the baseline assessments in one visit.

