8. PROCESS EVALUATION

The process evaluation will explore in detail, the feasibility and acceptability of both the intervention, and the study design and it will be conducted following the Medical Research Council guidelines for process evaluation of complex interventions. (64) We will develop a Process Evaluation Framework and Qualitative Analysis Plan to guide data collection and

analyses. A key aim of the process evaluation will be to assess and refine the programme theory in preparation for a full trial. In addition, it will assess: (i) intervention elements, i.e. acceptability, context, fidelity, exposure, reach and (ii) study related elements i.e. acceptability of study methods including recruitment, outcome measures and contamination.

Quantitative process data will include attendance at sessions and fidelity assessments. The fidelity assessment will be completed using randomly selected audio and video recorded sessions and a fidelity checklist developed by the study team, building on methods used in our prior intervention studies.(65) We will assess 24 individual initial assessments and 24 followup/discharge visits (n=8 per site). We will assess (by direct observation/researcher site visit) 6-9 of the group exercise sessions (2-3 visits per site), these will include a mixture of early, mid and late sessions per group. Finally, we will audio record all (where possible and where all participants of the group have consented) of the 'Health and Wellbeing' self care support sessions and assess a sample of 24-30 of these (8-10 per site), reflecting the full range of session-topics. Two team members will rate these sessions and inter-rater reliability will be assessed using Gwet's AC1. (66) We will also: (i) ask therapists to report confirmation that intended content (exercises, self-care topics, facilitation techniques) were taught, (ii) ask therapists to report both clinic observations of adherence to exercise and their assessment of home exercises performed by patients unsupervised, and (iii) patient reports of exercise adherence (based on completion of a weekly Progress Tracker diary during the first 12 weeks of the intervention). (67) Quantitative process evaluation data will be presented descriptively using mean (standard deviation) and median (interguartile range) for continuous variables and count (percentage) for categorical variables.

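### Assessor blinding is judged only from recorded blind breaks, with no question put to the assessor at each 3-month visit, so a low count cannot show that blinded assessment is achievable

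*Protocol*

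**What the plan says.** Section 2.1.2 lists the objective "To assess risks of bias/contamination". The Trial Summary repeats it as a secondary feasibility objective and gives its outcome measure as "Outcome blinding breaks and access to PERFORM intervention by control group". Section 2.4.3 puts the blinding half into practice in one sentence: "Any outcome assessor blind breaks will be recorded". The contamination half is handled differently. Control participants are to be asked whether they knew anyone in the intervention arm and whether they had access to its resources.

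The standard to be met is in section 6.8.3: "All outcome measures will be conducted by a blinded assessor who will have no knowledge of previous test results or treatment allocation".

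Section 8 sets the scope of the process evaluation for study methods as "acceptability of study methods including recruitment, outcome measures and contamination". Assessor blinding is not in that list. The protocol gives no definition of a break, no per-visit query to the assessor, and no criterion for judging whether blinding worked.

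**The concern.** Contamination is asked about; blinding is only logged when someone reports a break. A control participant who answers no to the contamination question supplies information. A 3-month visit with no break report supplies none, because it could mean that the assessor stayed blind, suspected the arm and said nothing, or knew it and did not report it.

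The setting makes unreported unblinding plausible. Participants know their allocation. Sites are existing rehabilitation centres. The follow-up battery includes an exercise adherence scale, and the answers may point to the arm without anyone disclosing it.

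What is at stake is limited but real. The incremental shuttle walk, 4-metre gait speed, grip strength and MoCA are conducted by an assessor and may be carried into the full trial. A feasibility study is the natural place to learn whether section 6.8.3 can be honoured in practice. As fixed, the protocol could end with a small number of breaks and no means of saying what that number shows.

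**Working it through.** The protocol states no figure for blinding, so there is none to reproduce. The check has three parts.

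**1. What is collected.** The references to blinding in the Trial Summary and sections 2.4.3 and 6.8.3 agree with one another: a blinded assessor is required and breaks are recorded. None adds a question to the assessor at each visit. Section 8 does not fill the gap.

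**2. Routes by which an assessor could learn or infer the arm.**
- The Exercise Adherence Rating Scale is part of the 3-month battery (sections 2.4.1 and 6.8.3).
- Questionnaires may be "completed under supervision or with a healthcare professional as necessary". This stands in the baseline section, but the same measures are repeated at follow-up.
- Section 4 has the local investigator "supported by a research nurse/fellow and/or relevantly trained rehabilitation staff at each site". It does not assign these staff to the follow-up assessment.
- Discharge visits, which only the intervention arm has, overlap the follow-up window. The programme starts within 4 weeks of randomisation and lasts 8 weeks, and discharge usually follows 1 to 2 weeks later. That runs from 0 + 8 + 1 = week 9 to 4 + 8 + 2 = week 14. Follow-up is at 3 months (about week 13) ± 4 weeks, so weeks 9 to 17.

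These are routes, not evidence that unblinding will occur.

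**3. What a count of zero could show.** Inputs: 60 participants randomised 2:1 (40 and 20) and 20% anticipated loss at 3 months (section 10.1). Assuming equal loss in both arms, 40 × 0.8 = 32 and 20 × 0.8 = 16, so 48 are assessed. The share of unblinded assessments that gets reported, s, is not in the protocol and is varied here as an assumption.

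The exact two-sided 95% upper limit for zero events in 48 is 1 − 0.025^(1/48) = 7.4%. This bounds recorded breaks. The corresponding bound on true unblinding is 7.4% / s:

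| Assumed share reported (s) | Upper limit on true unblinding |
|---|---|
| 100% | 7.4% |
| 50% | 14.8% |
| 25% | 29.6% |
| 10% | 74.0% |

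Conversely, if a share u of assessments is truly unblinded, the chance of recording no break is (1 − u × s)^48. With u = 25%:

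| Assumed share reported (s) | Chance of zero recorded breaks |
|---|---|
| 25% | 4.5% |
| 10% | 29.7% |
| 5% | 54.7% |
| 0% | 100% |

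Both tables treat visits as independent. The reading of a zero depends almost wholly on s, which the planned data do not reveal.

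**The case against.** The strongest reply is that the protocol is coherent: it requires a blinded assessor and records any break. On this view an extra item is a preference, and not a clean measure either, since a suspected allocation partly reflects how well the patient seems to have done. That limitation stands and belongs with the fix.

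Several stronger readings are tempting, and the documents do not support them.
- A reader might infer that an assessor who works out the arm will certainly go unrecorded. Section 2.4.3 does not confine breaks to overt disclosure, and a diligent assessor could log an inference. The supportable statement is that nothing in the protocol captures it systematically.
- A reader might infer that the plan would treat zero breaks as proof of blinding. It sets no threshold and says nothing of the kind. The difficulty is only that breaks are the sole blinding evidence specified.
- A reader might infer from section 4 that programme staff will do the follow-up tests. Section 6.8.3 bars any assessor who knows the allocation.
- A reader might think the result affects the decision to proceed. Blinding is not among the progression criteria in section 2.2, and EQ-5D, named in section 10.2.1 as the proposed primary outcome of the full trial, is reported by patients who know their arm.

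It is also fair to say that the CRFs and the Data Management Plan are not shown and might already hold a per-visit field. If so, the protocol only needs to say so. The matter cannot be left to the statistical analysis plan, because an analysis plan cannot recover answers that were never collected.

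**Conclusion.** The point holds as a minor improvement to data collection. For assessor blinding, the bias objective rests on a passive log of an undefined event, and a low count cannot show that the assessment required in section 6.8.3 is achievable. The tables give the size: zero breaks in about 48 visits is compatible with true unblinding of up to 7.4% under complete reporting and up to 74.0% if one instance in ten is reported. The reporting shares, equal loss in the two arms and independence between visits are assumptions. The conclusion itself needs only that reporting may be incomplete.

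The consequence is confined to the shuttle walk, gait speed, grip strength and MoCA. No progression decision changes, and nothing here shows that blinding will fail.

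**What to change.** Keep the break log and define a break. Add one CRF item, completed by the assessor after the last test of every 3-month visit:
- whether they know or suspect the allocation: intervention, control or don't know;
- why: told, saw, inferred or none.

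Count told and saw as breaks. Report all answers by arm with the number of visits assessed, about 32 and 16 on the protocol's own attrition figure. Reporting by arm matters because, with 2:1 allocation, an assessor who always answered intervention would be right 40/60 = 66.7% of the time. That caution applies to the new item, not to the break count.

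Any blinding index should be descriptive only. The arms are small, some answers will be don't know, and answers may cluster by assessor, so simple binomial intervals would be only a rough guide.

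The cost is one item at each of about 48 visits and one table. The drawback is that suspicion partly reflects perceived improvement, which the reason field separates only in part.
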